## 1 INTRODUCTION

This Statistical Analysis Plan (SAP) is based on the study protocol MMED007, final version 5.0, dated 10 February 2022.

The purpose of this document is to provide details concerning the data analyses and presentation of the study data in line with the objectives of the study. All the definitions, derivation rules and handling of missing data procedures will be detailed as well as references to the variables and datasets provided; details regarding efficacy analysis will be given.

Table, figure and listing layouts will also be provided in this document.

## 2 TRIAL DESIGN, STUDY DOCUMENTS, DATABASE CODING

### 2.1 TRIAL DESIGN

#### 2.1.1 Trial design

This is a randomized, double-blind, placebo-controlled, Phase 2a study on the efficacy and safety of repeated low dose D-lysergic acid diethylamide (LSD) D-Tartrate (MM-120) in adult subjects aged  $\geq 18$  and  $\leq 65$  with attention-deficit/hyperactivity disorder (ADHD).

Eligible subjects that consent to participate will be randomized in a 1:1 allocation to placebo or MM-120.

There will be 2 arms:

- Arm 1-Placebo: a total of 26 subjects will receive a placebo identical in appearance to the IMP administered orally twice weekly for 6 weeks. Subjects and site staff will remain blinded to the treatment group.
- Arm 2-MM-120: a total of 26 subjects will receive 20  $\mu$ g of MM-120 twice weekly for 6 weeks. Subjects and site staff will remain blinded to the treatment group.

Potential study subjects who provide informed consent will have eligibility evaluated/confirmed at 2 visits: 1) Screening, and 2) Baseline. The screening visit occurs up to 4 weeks prior to Baseline. An assessment will be made to confirm or make the ADHD diagnosis with the Mini International Neuropsychiatric Interview (MINI). The subject must have an Adult Attention Deficit Investigator Symptom Rating Scale (AISRS) score of  $\geq 26$  and a Clinical Global Impression - Severity of Illness Scale (CGI-S) score of  $\geq 4$  at screening and must meet all other eligibility criteria:

#### *Inclusion criteria*

1. Ability and willingness to provide written, informed consent prior to initiation of any study-related procedures and to adhere to all study requirements.  
NOTE: The subject (i.e., not a legally authorized representative) must be cognitively able to understand the requirements of the study and provide the informed consent.
2. Age  $\geq 18$  and  $\leq 65$  years at Screening.

3. Subjects with the diagnosis of Diagnostic and Statistical Manual of Mental Disorders-5 (DSM-5) ADHD, as determined by clinical evaluation and confirmed by structured interview (MINI).
4. AISRS total score of  $\geq 26$  at screening.
5. CGI-S score of  $\geq 4$  at screening.
6. Must be willing to receive IMP dose twice weekly. On Day 1, the subject will come to the clinic and must be willing to take a taxi or public transportation home or be accompanied by a caregiver and not drive a car, use heavy equipment, or participate in any other dangerous activity for the remainder of the day after receiving IMP (NOTE: at any protocol visit after Day 1 dosing, dosing visits may occur at the subject's home at the discretion of the PI, conducted by one of the study investigators or delegate and administered under supervision followed by the performance of the same procedures done at the clinic including safety monitoring. If early withdrawal is considered due to any safety issue identified, the Sponsor's medical monitor should be notified. If a remote visit is conducted due to any reason related to the COVID-19 pandemic, notification must be sent to the Medical Monitor's dedicated email address and Urgent Safety Measures as outlined in this protocol must be followed.)
7. Must be willing to refrain from more than 6 standard alcoholic drinks per week (1 standard drink corresponds to 0.1 L wine, 0.3 L beer, or 4 cL liquor), more than 10 cigarettes a day, and more than 2 cups of coffee a day throughout the study treatment period (6 weeks) and until the last study visit is complete (EOS or ET).

#### *Exclusion criteria*

1. Past or present diagnosis of a primary psychotic disorder or first-degree relative with a psychotic disorder.
2. Past or present bipolar disorder (DSM-5).
3. Other current psychiatric disorders that, in the opinion of the Investigator or medical supervisor, may confound the results of the study (e.g., obsessive-compulsive disorder, dysthymic disorder, panic disorder, dissociative disorder, anorexia nervosa or bulimia nervosa).
4. Subjects with [REDACTED] substance use disorder (except nicotine, provided subject does not smoke [REDACTED])
5. Somatic disorders including Central Nervous System (CNS) involvement of cancer, severe cardiovascular disease, untreated hypertension, severe liver disease (liver enzyme increase by more than 3x the upper limit of normal except unconjugated hyperbilirubinemia due to Gilbert's Disease, per Investigator), severely impaired renal function (estimated creatinine clearance  $< 50$  mL/min by CKD-EPI formula), or anything else that, in the judgment of the Investigator or medical supervisor, poses too great a potential for side effects.
6. Any lifetime history of suicide attempt; [REDACTED] active suicidal thoughts or ideation (defined as a suicidal ideation score of 2 or greater in the Columbia-Suicide Severity Rating Scale [C-SSRS]); or endorsement of any suicidal behavior on the C-SSRS within the [REDACTED] the screening visit.

7. Likely to require psychiatric hospitalization during the course of the study.
8. Once consent is signed, subject not willing or able to stop any prescription or nonprescription ADHD medications during screening and prior to the baseline visit through final study visit (EOS or ET). *A list of prohibited medications is provided in APPENDIX C.*
9. Plan to start, stop, or alter the use of any medications, supplements, or other therapeutics from Baseline until EOS or ET (see Appendix 1 for list of prohibited medications).
10. Plan to start, stop or alter the use of psychotherapy, massage, meditation, acupuncture, hypnosis, yoga, or other similar therapy/activity from the time of providing informed consent until EOS or ET.
11. [REDACTED]
12. Likely to need use of any psychiatric medications with the potential to confound interpretation of study results or impact safety, at the discretion of the Investigator, in the 10 weeks following Baseline up to EOS or ET (see APPENDIX C for list of prohibited medications).
13. Use of investigational medication/treatment in the past 30 days prior to the screening visit.
14. [REDACTED]
15. Clinically significant abnormal baseline laboratory values, VSs, and ECG that include the following:
  - a. Have evidence of clinically significant hepatic disorder (e.g., alanine aminotransferase [ALT] or aspartate aminotransferase [AST] > 3X ULN (except for Gilbert's disease), and
  - b. Any clinically significant abnormal metabolic or hematologic screen, per Investigator or medical supervisor decision
  - c. Exclusionary blood pressure: >140 mm Hg (systolic) or >90 mm Hg (diastolic); heart rate <45 beats/minute or >90 beats/minute after an approximately 5- minute supine or semi-supine rest NOTE: If the first measurement of a subject's heart rate is > 90 beats/minute, a second recording is allowed after an additional approximately 5-minute supine rest
  - d. Exclusionary ECG parameters: QTcF > 450 msec (men), QTcF >470 msec (women)
  - e. Any clinically significant abnormal electrocardiogram (ECG) finding (e.g., uncontrolled atrial fibrillation, ischemia) at Screening (Visit 1) or Baseline (Visit 2), as determined by the Investigator or medical supervisor (in consultation with a cardiologist, if needed).
16. Any other condition, therapy, laboratory abnormality, or other circumstance that, in the opinion of the Investigator or medical supervisor, may pose additional risk to the subject from participation in the study, may interfere with the subject's ability to comply with study procedures, may make participation in the study not in the subject's best interest or may confound the results of the study.
17. Prior history or ongoing neuropsychiatric signs or symptoms associated with COVID-19 such as development of, or current disorder, during or after a

COVID-19 infection including anxiety, memory loss, confusion, depression, delirium, agitation, or psychosis.

18. Women of childbearing potential (WOCBP) (i.e., physiologically capable of becoming pregnant) who are unwilling or unable to use a highly effective method of contraception, (see Protocol Appendix 2) for the duration of the study, OR Men physiologically capable of fathering a child who are sexually active with WOCBP but are unwilling or unable to use barrier contraception (e.g., condom with or without spermicidal cream or jelly) for the duration of the study. NOTE: See Protocol Appendix 2 for definitions of WOCBP and highly effective methods of contraception and for information about unacceptable methods of contraception.
19. Women who are currently pregnant or breastfeeding or plan to become pregnant or breastfeed during the study.
20. Men who plan to donate sperm during the study.
21. Use of weight loss drugs [REDACTED] of screening until the end of study.
22. Subjects who are either unable or unwilling to consume alcohol in any amount (including due to religious or personal reasons).
23. Subjects who have a change in AISRS score of  $\geq 13$ -points between screening and baseline visits.

The baseline visit will occur on the clinic day before Day 1 and will confirm AISRS score. If there is a  $\geq 13$ -point change in the AISRS between the screening visit assessment and the baseline assessment, or if the subject does not return for the baseline AISRS, the subject will not be randomized, and will be terminated from the study. Eligible subjects will be randomized at Day 1 to either 20  $\mu$ g of MM-120 or to matching placebo and begin the double-blind treatment period on Day 1.

[figure not shown]
Double-blind treatment period:

The double-blind treatment period will last 6 weeks, with dosing twice weekly (every 3 to 4 days). Day 1 will be the first day of dosing. At the end of the 6 weeks-treatment period, subjects will be assessed by a study physician. All subjects and site staff will remain blinded to the treatment group.

Subjects will be provided with a diary in which the sleep quality/ duration rating data will be recorded.

Follow-up:

There will be a single follow-up visit 4 weeks after the last double-blind treatment visit (i.e., at Week 10).

**Figure 1. Study Schedule Diagram**

## 2.1.2 Schedule of assessments and visit windows

Table 1 reports full details on the schedule of assessments.

For all measurements, the actual date and time of assessment, including date of sampling, will be recorded in the eCRF.

**Table 1: Schedule for study specific assessments.**

Time in Weeks	Screening	Baseline g	Dosing beginning	Dosing Period (20 µg MM-120) h 6-week Blinded Treatment				End of Study/ Early Termination h
Arm 1 - placebo Arm 2-MM-120	Up to 4 weeks prior to Day -1	Day -1	Day 1	Week 2 (Pre-dose on 3 rd dosing visit) Day 8 (+/- 1 day)	Twice weekly* Dosing (+/- 1 day) (Starts Day 1)	Every 2 weeks (first dose of the week) (Starts Day 15)	Week 6 (before final dose unless otherwise noted)	Week 10 follow-up or final visit if withdrawing from study
Informed consent	X							
Demography	X							
Medical/surgical history	X							
Inclusion/exclusion criteria	X	X						
Pregnancy test (for women without documentation of sterilization)	X		X		X 			X
Physical examination	X						X	X
Weight and BMI a	X						X	X
Height	X						X	X
Vital signs b	X	X	X		X		X	X
Clinical Laboratory Tests c	X					X	X	X
Pharmacokinetics			X 					
████████	████	████	████		████	████		
Pharmacodynamics (5D- ASC, & MEQ30) d			X				X 	
12-lead ECG e	X		X 				X 	
Cognitive Performance Test		X					X	
CAARS f	X	X				X	X	X

Time in Weeks	Screening	Baseline g	Dosing begins	Dosing Period (20 µg MM-120) h 6-week Blinded Treatment				End of Study/ Early Termination h
Arm 1 - placebo Arm 2 – MM-120	Up to 4 weeks prior to Day -1	Day -1	Day 1	Week 2 (Pre-dose on 3 rd dosing visit) Day 8 (+/- 1 day)	Twice weekly* Dosing (+/- 1 day) (Starts Day 1)	Every 2 weeks (first dose of the week) (Starts Day 15)	Week 6 (before final dose unless otherwise noted)	Week 10 follow-up or final visit if withdrawing from study
ASRS (done prior to dosing)		X				X	X	X
AISRS, CGI-S	X	X		X			X	X
MINI	X							
C-SSRS screening/baseline	X							
C-SSRS since last visit (SLV)		X	X		X		X	X
VAS				X 				
Check daily diary	X	X	X		X		X	X
Randomization			X					
MM-120 or placebo administration			X		X 			
Adverse events	X	X	X		X		X	X
Concomitant medication	X	X	X		X		X	X
Blood sample collection for biobanking (PGX analysis)	X If the subject gives informed consent to provide a pharmacogenomic sample, collect a sample once during the study							

Abbreviations: 5D-ASC = 5 dimensions of altered states of consciousness scale; AISRS = Adult ADHD Investigator Symptom Rating Scale; ASRS = Adult ADHD Self-Report Scale; BMI = body mass index; BP = blood pressure; CAARS = Conners' Adult ADHD Rating Scale; CGI-S = Clinical Global Impression Scale; C-SSRS = Columbia-Suicide Severity Rating Scale; ECG = electrocardiogram; MEQ30 = Mystical Experience Questionnaire (30-item); PGX = pharmacogenomics; VAS = Visual Analog Scale.

\*Twice weekly dosing will occur every 3 to 4 days (e.g., every Monday and Wednesday) with a  $\pm$  1 day window and will be coordinated to occur at the same time as the Week 2 visit and the every 2 weeks visits when possible.

- a Body mass index will be calculated using body height at screening.
- b Vital signs (pulse, BP, HR, RR, and body temperature) will be performed at every visit.
- c Clinical laboratory samples for chemistry and hematology and urine samples for [REDACTED] and pregnancy testing will be collected pre-dose.
- d Pharmacodynamic scales are completed at home up to 6 hours after dosing.
- e Subject should be supine for 5 minutes prior to ECG collection.
- f CAARS-S-OR conducted at screening. All other assessments will be with the CAARS-L-SR.

g Baseline visit is within 3 days of Day 1 ( $\pm 1$  day).

h Following day 1 dosing, all visits may be conducted remotely per Investigator decision as long as all activities can be conducted per protocol, e.g., calibrated blood pressure cuff, calibrated weight scale, ECG, computer cognitive scale. Any visit conducted remotely due to COVID-19 requires Sponsor Medical Monitor and operations team notification and conduct under urgent safety measures and all protocol deviations captured in EDC designated COVID-19 deviation.

X subject fills out forms at home.

█

X 6 weeks of blinded treatment on MM-120 / placebo; may be dosed at home per Investigator decision.

X 2 hours after dosing.

X 6 hours after dosing.

X Collected repeatedly 0-6 hours after dosing.

X PK samples will be collected at pre-dose, 0.5, 1, 2, 3, 4, and 6 hours post-dose.

X During treatment period, pregnancy testing will occur predose at each dosing visit or a minimum of once weekly. All pregnancy test results are being recorded on the subject's source document (paper record). The pregnancy test results are not entered into the eCRF for weeks 3, 5, and 6.

### **2.1.3 Visit windows**

As subjects do not always adhere to the protocol visit schedule, the following rules will be applied to assign actual visits to analysis visits for all parameters.

The visit windows and the target days for each visit (including unscheduled ones) are listed below in Table 2. The reference day is Day 1, the first day of dosing, as defined in Section 11.1.1. If a subject has two or more actual visits in the same visit window, the visit closest to the target day will be used for recording data from that visit in the EDC. The data collected scheduled and unscheduled visit(s) will be mapped to visits as follows: If two actual visits are equidistant from the target day within a visit window, the later visit will be used; if more than one value falls on the same day then the last sequential number in sdtm will be used.

All assessments corresponding to both scheduled and unscheduled visits will be included in subject listings.

Table 2 contains analysis visit windows and the target study days for the following selected visits: Baseline, Week 2, Week 4, Week 6 and Week 10; lower and upper limits associated with each visit will cover all possible days from randomization to end of study allowing mapping all the applicable assessments to the visits.

As vital signs and Columbia-Suicide Severity Rating Scale (C-SSRS) will be evaluated at each visit (twice weekly), a different time windowing will be applied to those variables only (see Table 3). Daily diary contains daily sleep quality/ duration rating assessments that will be computed at each week by the mean of values recorded between lower and upper limits (days) specified in Table 4, no target study day will be considered.

For parameters, where Time Interval Upper Limit for Baseline is equal to 1, please apply a rule of time defined in section 11.1.1.8 for Baseline.

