7.8.1. Adverse events documentation

AEs will be described and recorded on the subject's eCRF, regardless of the severity or relationship to the IMP. AEs are rated for severity, and the potential relationship regarding the study interventions will be evaluated by the Investigator according to standard criteria. Subjects with AEs will be treated appropriately. Abnormal laboratory values not explained by the subjects' disease will be repeated until normal, or until the abnormality can be explained, and the subject's safety is not at risk.

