### ***8.11.3.2 Chemistry***

- Albumin;
- Total protein;
- Alkaline phosphatase;
- ALT;
- AST;
- Bilirubin, total;
- Chloride;

- Creatinine;
- Creatinine clearance (CKD-EPI);
- FSH (follicle stimulating hormone);
- GGT (gamma-glutamyl transferase);
- C Reactive Protein;
- Glucose;
- Lactate dehydrogenase;
- Blood urea nitrogen or urea;
- Phosphate;
- Potassium;
- Calcium;
- Sodium.

In addition, a [REDACTED] and a urine pregnancy test, only in women, will be performed at selected time points (Baseline, Week 2, Week 4, Week 6, Week10) before IP dosing throughout the study (see Section 2.1.2).

The definitions of marked abnormalities in SI units are provided in Table 5 and Table 6 below.

The columns labelled "L", "LL", "H" and "HH" display the increasing grade (severity) of abnormally low ("L", "LL"), or high values ("H", and "HH") for each of the laboratory parameters listed in the first column, as appropriate.

Treatment-emergent MLAs are those occurring after the study treatment start and up to study treatment discontinuation, that were not present at baseline in the same or worse category (considering the direction of worsening). In other words, the MLAs are evaluated independently by direction of worsening (e.g., a post-baseline MLA of "HH" is considered treatment-emergent if the baseline is "L" or "LL" (where applicable) or "H", or within normal limits or missing. On the other hand, it is not considered as treatment-emergent if the baseline is "HH" when applicable).

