### **10.12.4 Laboratory**

Clinical laboratory data, abnormalities (defined in section 8.11.3) will be summarized on SAF.

The percentage of subjects with values beyond clinically important limits will be summarized by frequency tables and shift tables (Normal, Abnormal not clinically significant, Abnormal clinically significant), as well as the abnormalities in general. Data will be also summarized for the absolute value and corresponding change from baseline at each scheduled assessment, using respective SI units.

Individual listings will be produced for all parameters reporting flags of abnormal or out-of-range values.

Listings of pregnancy test results will be presented.

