#### 12.8.5 Laboratory

Output name	Display*	Title (Description)	Analysis set(s)**	Key deliverable	Mock layout	SAP section
LAB	S	Change from Baseline over time by laboratory parameters (SI unit)	SAF		Layout T22	
LABABN	S	Summary of clinical laboratory abnormalities (beyond clinically important limits) by visit	SAF		Layout T28	
SHIFTLABBN	S	Shift table of clinical laboratory abnormalities by visit	SAF		Layout T29	10.12.4
LAB	L	Listing of laboratory parameters, with abnormal or out-of-range values flagged	SAF		Layout L12	
LPT	L	Listing of pregnancy test results	SAF		Layout L13	

\* S=Summary table, L= Listing, F=Figure, \*\* SCR=Screened set, FAS=Full Analysis set, SAF=Safety set, RAN=Randomized set, PPS=Per protocol set, PKS=Pharmacokinetic analysis set

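### One laboratory value per visit window feeds the abnormality tables, so some marked abnormalities can drop out of the reported percentages, and treatment-emergent ones are defined but never tabulated

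*SAP*

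**What the plan says.** SAP 2.1.3 states that "the following rules will be applied to assign actual visits to analysis visits for all parameters", and laboratory data are given no exception. Three selection steps follow:

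- Several visits in one window: "If a subject has two or more actual visits in the same visit window, the visit closest to the target day will be used". The sentence ends with a loosely worded reference to EDC recording, but the opening of the section and the tie rule show that it governs analysis-visit mapping.
- Ties: "If two actual visits are equidistant from the target day within a visit window, the later visit will be used".
- Same day: "if more than one value falls on the same day then the last sequential number in sdtm will be used".

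Unscheduled visits are mapped by the same rules.

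On repeat testing, Protocol 7.8.1 says that abnormal values not explained by the subject's disease "will be repeated until normal, or until the abnormality can be explained".

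On reporting, SAP 10.12.4 promises: "The percentage of subjects with values beyond clinically important limits will be summarized by frequency tables and shift tables". SAP 12.8.5 lists two abnormality outputs. LABABN (layout T28) is titled "Summary of clinical laboratory abnormalities (beyond clinically important limits) by visit", and SHIFTLABBN (layout T29) is also by visit. SAP 8.11.3.2 adds a definition that spans the whole treatment period: "Treatment-emergent MLAs are those occurring after the study treatment start and up to study treatment discontinuation".

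**The concern.** A nearest-to-target rule suits means and changes from baseline, where one representative value per subject and visit is wanted. It does not suit a count of subjects who crossed a safety limit, because there the extreme value is the information. The protocol plans repeat testing after unexplained abnormal results, so pairs of an abnormal value followed by a normal one are to be expected in the data. Two of the three selection steps (tie and same day) favour the later member of such a pair.

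At stake is the percentage of subjects beyond clinically important limits, which Protocol 12.1 and 13.6.7.2 and SAP 10.12.4 all promise. In a small trial of a new indication, a single subject with a marked liver enzyme elevation is something a reader of the summary tables should be able to see.

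**Working it through.** The plan states no figure to reproduce. The check applies the selection rule to the laboratory windows and asks which value reaches T28 and T29.

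**Inputs**
- Windows (SAP Table 2, laboratory): Week 2 is Days 2–21, target 15. Week 4 is Days 22–35, target 29. Week 6 is Day 36 to EOT, target 43. Week 10 is from EOT+1, target 70.
- EOT is the date of the last dose (SAP 11.1.1.3), planned for Day 40.
- Scheduled tests: every two weeks from Day 15, then Week 6 and Week 10 (SAP Table 1). The Week 6 sample is taken before the final dose at the last-dose visit (Protocol 6.2.4.4). Dosing visits have a ±1 day window.

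**Rule**: select the value that minimises |day − target|. If equal, take the later day. If the same day, take the last sequence number.

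**Results** (planned EOT, Day 40)

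| Window | Abnormal value | Other value | Distances | Value tabulated |
|---|---|---|---|---|
| Week 2 | Day 14 | Day 15 | 1 vs 0 | other |
| Week 2 | Day 14 | Day 16 | 1 vs 1, tie | other (later) |
| Week 2 | Day 14 | Days 17–21 | 1 vs 2–6 | abnormal |
| Week 2 | Day 15 | Days 16–21 | 0 vs 1–6 | abnormal |
| Week 2 | Day 16 | Days 17–21 | 1 vs 2–6 | abnormal |
| Week 2 | Day 8, unscheduled | Day 15, scheduled | 7 vs 0 | other |
| Week 4 | Day 28 | Day 29 or 30 | 1 vs 0 or 1 | other |
| Week 4 | Day 29 | Days 30–35 | 0 vs 1–6 | abnormal |
| Week 4 | Day 30 | Days 31–35 | 1 vs 2–6 | abnormal |
| Week 6 | Days 36–39 | any later day to Day 40 | e.g. 7 vs 3 | other |
| Week 6 | Day 40 (EOT) | Day 41 or later | different windows | abnormal |
| Week 10 | Days 41–67 | Day 68 | 29–3 vs 2 | other |

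Four points follow.

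1. In the Week 2 and Week 4 windows, an unscheduled abnormal value on any day other than the target is displaced by a scheduled test on Day 15 or Day 29.
2. In the Week 6 window the distances to Day 43 fall steadily (7, 6, 5, 4, 3 for Days 36 to 40), so the last value in the window always wins. This holds for EOT on Days 39 to 43. With EOT on Day 44 the one exception is the pair Day 43/Day 44.
3. In any window, a same-day repeat replaces the first value, assuming that the repeat carries the higher sequence number.
4. The selected value is one of the values in the window. Subjects whose selected value is beyond a limit are therefore a subset of those with any value beyond it. The selected-value percentage can equal or fall below the any-value percentage, but cannot exceed it.

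**Size per subject**: with 26 per arm, all dosed, 1/26 = 3.8 percentage points.

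**Outputs**: SAP 12.8.5 lists a change-from-baseline table, LABABN, SHIFTLABBN and two listings. Layouts T28 and T29 have no any-time row, and no output counts treatment-emergent marked abnormalities, although Appendix B records that their definition was added in version 2.0. By contrast, SAP 12.8.3 does list a treatment-emergent ECG table (ECGTEA).

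**The case against.** The strongest reply is that the ordinary case is safe. Scheduled tests fall on Days 15 and 29, which are the targets, so a later-day repeat is farther away and the abnormal value is kept. For a subject on schedule, the Week 6 sample is drawn on the EOT date itself, so a repeat on a later day belongs to the Week 10 window and cannot displace it. A reader might infer from the Day 43 target that every abnormal Week 6 result with a repeat is lost, or that a repeat always wins because it comes later. The documents support neither inference. At Week 6 the exposure is limited to same-day repeats and to values on Days 36–39 followed by another test on or before EOT.

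A reader might also infer that a displaced abnormality survives only in a listing. That goes too far. Protocol 7.6.1 counts an abnormal laboratory finding as a possible adverse event, the adverse event tables do not use visit-window selection, and Protocol 12.2 has a medically qualified expert review laboratory data for other significant events. Repeats are also limited to values the disease does not explain, and may stop once an explanation is found.

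Finally, neither document promises worst-value tables, the promised frequency and shift tables are provided, and no inference on safety is planned. All of this stands, and it narrows the point. It does not close the gap: adverse event reporting depends on an investigator's judgement, listings give no percentage, and the treatment-emergent definition in SAP 8.11.3.2 still has no table.

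**Conclusion.** The point holds in a limited form. As written, the plan can drop some marked laboratory abnormalities from T28 and T29 in three situations:

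- same-day repeats;
- unscheduled abnormal values away from the target day, including those on Days 36–39 followed by a later test on or before EOT, and those after EOT followed by a test nearer Day 70;
- scheduled tests done a day early and repeated on the target day or the day after.

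The reported percentage can therefore be understated but is not always, and it cannot be overstated. The documents do not show how often this would occur, so 3.8 percentage points per lost subject is a unit of effect and not an estimate of bias. It assumes 26 dosed subjects per arm. Separately, and whatever the timing of repeats, treatment-emergent marked abnormalities are defined but not tabulated. The primary efficacy analysis is unaffected.

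**What to change.** Three changes to the SAP:

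1. In 2.1.3, restrict the nearest-to-target, tie and same-day rules for laboratory data to means and changes from baseline.
2. For T28 use each subject's worst value (in each direction where applicable), and for T29 the worst category, among all scheduled and unscheduled results in the window.
3. Add to T28 one overall on-treatment row per parameter that counts subjects with any treatment-emergent marked abnormality as defined in 8.11.3.2.

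The cost is SAP wording and minor programming, using results already collected. Abnormality rates may look slightly less favourable in both arms.
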